6.6 HANDLING OF MISSING DATA AND OUTLIERS

Missing or incomplete AE dates are imputed according to BI standards (see "Handling of Missing and Incomplete AE Dates"). (2)

No imputation will be performed in efficacy and safety analyses.

Missing or partial date information will be replaced according to following rules.

YEAR	MONTH	DAY	YMD	DT
"Unknow	n" (tick-box)	UNKNOWN		
<2007	Null	Null	2007	2007/07/01
уууу	Null or "Unknown"	Null	уууу	yyyy/07/01
уууу	Mm	Null or "Unknown"	yyyymm	yyyy/mm/15
уууу	Mm	"First ten days of the month"	yyyymm "First ten days of the month"	yyyy/mm/01
уууу	Mm	"Second ten days of the month"	yyyymm "Second ten days of the month"	yyyy/mm/11
уууу	Mm	"Third ten days of the month"	yyyymm "Third ten days of the month"	yyyy/mm/21

If the date of data which is collected as after treatment of Trazenta[®] in the CRF is before start of Trazenta[®], these data are regarded as erroneous and will be set to missing.

6.7 BASELINE, TIME WINDOWS AND CALCULATED VISITS

With regard to efficacy and safety endpoints, the term "baseline" refers to the last observed measurement prior to administration of Trazenta[®] including the first administration date.

Efficacy analyses will be performed based on calculated visits as shown in Table 6.7: 1. If two or more data points of a patient fall into the same interval, closest value to the planned day will be selected. If there are two observations which have the same difference in days to the planned day or if there are two observations on the same day, the first value will be used.

Table 6.7: 1 Baseline, time windows and calculated visits

		Time window (actual days on treatment)	
Week label	Planned days	Start	End
Baseline	0	NA	1
Week 12	84	2	133
Week 26	182	134	231
Week 40	280	232	322
Week 52	364	323	406
Week 64	448	407	497
Week 78	546	498	637
Week 104	728	638	819
Week 130	910	820	1001
Week 156	1092	1002	End of study

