5. VARIABLES AND THEIR ASSESSMENT

5.1 EFFICACY

5.1.1 Endpoints of efficacy

There is no primary endpoint for efficacy as the primary objective of a PMS is evaluating safety.

The secondary endpoint for this PMS is the change from baseline in HbA1c at the last observation during the observation period.

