4. CHANGES IN THE PLANNED ANALYSIS OF THE STUDY

There has been no change in the planned analysis from the statistical methods described in the NIS Protocol.

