5.2.2 Secondary endpoint(s)

The secondary endpoint will be used as stated in the NIS Protocol Section 5.1.1.

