6. GENERAL ANALYSIS DEFINITIONS

6.1 TREATMENT(S)

For basic study information on treatments, please refer to NIS Protocol Section 4. The technical specification for treatment set-up is described in the analysis data set (ADS) plan.

For efficacy analyses, data up to 7 days after last treatment intake will be considered as on treatment for HbA1c

For safety analyses, data up to 7 days after last treatment intake will be considered as on treatment for AE.

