7.5 SECONDARY ENDPOINT(S)

7.5.1 Key secondary endpoint(s)

This section is not applicable as no key secondary endpoint has been specified in the NIS protocol.

7.5.2 (Other) Secondary endpoint(s)

For the change from baseline in HbA1c at the last observation, descriptive statistics will be calculated by treatment (background medication and total). A 95% confidence interval for the mean change from baseline will also be calculated by treatment (background medication and total).

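### Could the SAP's visit windows replace the last on-treatment HbA1c with an earlier value?

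*SAP*

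**What the plan says.** Protocol 5.1.1 defines the secondary endpoint as the "change from baseline in HbA1c at the last observation during the observation period". The protocol synopsis adds that this observation is on treatment. SAP 5.2.2 adopts the definition: "The secondary endpoint will be used as stated in the NIS Protocol Section 5.1.1". SAP 7.5.2 gives the analysis: "For the change from baseline in HbA1c at the last observation, descriptive statistics will be calculated by treatment", with a 95% confidence interval for the mean change. SAP 6.1 sets the outer limit: "data up to 7 days after last treatment intake will be considered as on treatment for HbA1c". SAP 4 states: "There has been no change in the planned analysis from the statistical methods described in the NIS Protocol".

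SAP 6.7 then says: "Efficacy analyses will be performed based on calculated visits as shown in" Table 6.7: 1, which has a baseline row and nine post-baseline week labels. For several values in one window: "If two or more data points of a patient fall into the same interval, closest value to the planned day will be selected". For values equally far from the planned day, "or if there are two observations on the same day, the first value will be used". The table has no row for a last value, and neither 6.7 nor 7.5.2 gives the order of the two steps.

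**The concern.** The sentence in SAP 6.7 covers efficacy analyses without exception, and the last-observation change in HbA1c is the only efficacy analysis in the available text. A programmer could therefore reduce the data to one value per window first and then take the last filled window as the last observation. The rule favours nearness to the planned day, and the earlier value in a tie, so it can discard a patient's true last value.

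Two programmers could then derive different endpoint values for the same patient. One of the two results would not be the protocol's endpoint, although the SAP declares no change from the protocol.

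**Working it through.** **Inputs.** Planned days and window limits come from SAP Table 6.7: 1, the selection rule from SAP 6.7, and the on-treatment limit from SAP 6.1.

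**1. Reproduce the windows.** Each closed window ends midway between adjacent planned days: (84+182)/2 = 133, (182+280)/2 = 231, (280+364)/2 = 322, (364+448)/2 = 406, (448+546)/2 = 497, (546+728)/2 = 637, (728+910)/2 = 819, (910+1092)/2 = 1001. All eight match the table. The last window runs from day 1002 to the end of the study.

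**2. Apply the rule.** For two values on days d1 < d2 in a window with planned day p, the later one is kept only if |d2 − p| < |d1 − p|.

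| Days | Window (p) | Distances | Selected | Chronologically last |
|---|---|---|---|---|
| 160, 190 | Week 26 (182) | 22, 8 | 190 | 190 |
| 728, 800 | Week 104 (728) | 0, 72 | 728 | 800 |
| 700, 756 | Week 104 (728) | 28, 28 | 700 | 756 |
| 1092, 1130 | Week 156 (1092) | 0, 38 | 1092 | 1130 |

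So the two orders of operation can give different answers.

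**3. What can differ.** The windows run without gaps from day 2 to the end of the study. The last filled window is therefore always the one that holds the chronologically last value. Both orders use the same patients and draw from the same window. They differ only if that window holds two or more on-treatment values and the later one is as far from the planned day or farther.

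**4. How often.** The documents do not say. Take an extreme illustration: every visit on its planned day, a separate HbA1c at every stop, and stopping days uniform over days 2 to 1091 (1,090 days). The last value is then replaced whenever the stop falls after the planned day in its window. The number of such days is 49+49+42+42+49+91+91+91+0 = 504, and 504/1,090 = 46.2% of discontinuing patients. Among those replaced, the value used is on average 35.8 days earlier and at most 91.

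The share moves with the assumptions. It is 36.7% or 36.0% if all visits are 14 days early or late, 26.4% or 25.7% at 28 days early or late, and 0% if visits fall on planned days and no separate stop value exists. The 91-day maximum also rests on planned-day visits: days 638 and 819 lie 90 and 91 days from 728, so the rule would keep a value 819 − 638 = 181 days earlier. The Week 156 window has no fixed limit.

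The documents give no discontinuation rate and no HbA1c difference between such values, so no shift in the mean can be computed.

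**5. Is there a second value at stopping?** Protocol 6.1 lists discontinuation as an observation time in addition to the scheduled weeks. Against that, the flow chart gives discontinuation no column of its own (it shares the Week 156 column), and its footnote treats time points as approximate and assigns data to the closest visit. Protocol 3.1 offers the scheduled weeks or discontinuation. Protocol 6.2.3 ends the study at the Week 156 visit or at the last visit before stopping, with no follow-up. A routine extra value is therefore uncertain, and a second value after Week 156 is unlikely.

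**6. Which order does the text support?** SAP 6.7 assigns values to week labels. It does not define the last observation as the last filled label; the reader would have to add that. The endpoint's own wording is chronological in Protocol 5.1.1 and SAP 7.5.2, SAP 5.2.2 takes it over as it stands, and SAP 4 denies any change. SAP 6.3 also admits patients to the efficacy set on a baseline and one available on-treatment HbA1c, without reference to windows.

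**The case for a change.** The best case for a change is that the sentence in SAP 6.7 makes no exception for this endpoint. The same section spells out baseline as the last measurement up to and including the day of first administration, but gives the post-baseline last observation no matching rule. SAP 3 promises detailed procedures, SAP 6.7 itself expects several values in one window, and stating the order would cost a sentence or two.

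It stands that the order is not written down and that a programmer acting in good faith could window first. It does not stand that the SAP prescribes this, because the step from the last filled week label to the last observation appears nowhere. A specific endpoint definition, adopted by reference and declared unchanged, reasonably governs over a general sentence about visits.

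Nor does the windowing sentence have to be aimed at this endpoint. SAP 5.3 refers to further endpoints, although Protocol 5.1.1 names none, and Section 7.6 is not in the available text. By-visit HbA1c summaries there would give the sentence an obvious target. That cannot be confirmed, so the conclusion does not depend on it.

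**Conclusion.** No change follows. This is missing detail that analysts would fill correctly from the endpoint's own wording: the chronologically last HbA1c up to 7 days after last intake. An added sentence would only record that reading.

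On that reading the effect on the result is zero. On the other, the same patients are analysed, and some contribute an earlier on-treatment HbA1c from the same window. The 46.2% describes one favourable set of assumptions for discontinuing patients only and should not be taken as an estimate; the share falls to 0% with planned-day visits and no separate stop value. Neither the size nor the direction of any shift in the mean change can be derived from the documents.

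Little rests on it either way. The endpoint is secondary, and Protocol 7.2 describes the analyses as descriptive and exploratory, without formal inference. No error rate, sample size or safety result is affected. The conclusion assumes that nothing in the unavailable SAP sections defines the last observation as the last calculated visit.

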7. PLANNED ANALYSIS

For End-Of-Text tables, the set of summary statistics is: N / Mean / SD / Min / Median / Max.

For tables that are provided for endpoints with some extreme data, median, quartiles and percentiles should be preferred to mean, standard deviation, minimum and maximum

Tabulations of frequencies for categorical data will include all possible categories and will display the number of observations in a category as well as the percentage (%) relative to the respective treatment group (unless otherwise specified, all patients in the respective patient set whether they have non-missing values or not). Percentages will be rounded to two decimal places. The category missing will be displayed only if there are actually missing values.

Analyses will be performed for overall patients as one treatment group. In addition, same analyses by background medication groups as defined in Table 5.4 will be performed all analyses.

7.1 DEMOGRAPHIC AND OTHER BASELINE CHARACTERISTICS

Descriptive statistics for the demographic and other baseline characteristics described in Section 5.4 are planned by treatment (background medication and total).

7.2 CONCOMITANT DISEASES AND MEDICATION

Concomitant diseases will be coded by the latest version of Medical Dictionary for Regulatory Activities (MedDRA). Frequency of patients will be summarised by treatment (background medication and total), system organ class (SOC) and preferred term (PT).

Concomitant medication will be coded by latest version of "Nihon-iyakuhinshu".

7.3 TREATMENT COMPLIANCE

It is not planned the analysis for the treatment compliance.

7.4 PRIMARY ENDPOINT(S)

The incidence of adverse drug reactions (ADRs) will be evaluated descriptively as specified in Section 7.8.1.

7.5 SECONDARY ENDPOINT(S)

7.5.1 Key secondary endpoint(s)

This section is not applicable as no key secondary endpoint has been specified in the NIS protocol.

7.5.2 (Other) Secondary endpoint(s)

For the change from baseline in HbA1c at the last observation, descriptive statistics will be calculated by treatment (background medication and total). A 95% confidence interval for the mean change from baseline will also be calculated by treatment (background medication and total).

7.7 EXTENT OF EXPOSURE

Only descriptive statistics by treatment (background medication and total) are planned for this section of the report. The followings are the categories of exposure-ranges (in weeks):

>0 to 12 weeks, >12 to 26 weeks, >26 to 40 weeks, >40 to 52 weeks, >52 to 64 weeks, >64 to 78 weeks, >78 to 104 weeks, >104 to 130 weeks, >130 to 156 weeks, >156 weeks

7.8 SAFETY ANALYSIS

7.8.1 Adverse events

Unless otherwise specified, the analyses of adverse events (AEs) will be descriptive in nature. All analyses of AEs will be based on the number of patients with AEs and NOT on the number of AEs.

Furthermore, for analysis of AE attributes such as duration, severity, etc. multiple AE occurrence data on the case report form, will be collapsed into AE episodes provided that all of the following applies:

- The same MedDRA lowest level term was reported for the occurrences
- The occurrences were time-overlapping or time-adjacent (time-adjacency of 2 occurrences is given if the second occurrence started on the same day or on the day after the end of the first occurrence)
- Treatment did not change between the onset of the occurrences OR treatment changed between the onset of the occurrences, but no deterioration was observed for the later occurrence

For further details on summarization of AE data, please refer to the guideline 'Handling and summarization of adverse event data for clinical trial reports and integrated summaries' (1).

AE analyses will be carried out after integrating AE data from CRF and AE data from perceive system.

In addition, AEs coded as "no adverse event" will not be included in the AE analyses.

Two overall summaries of AEs will be presented. One will be also made for patients including those who were not treated add-on therapy at baseline (i.e. all patients with Trazenta® treatment). Another one will include patients only with add-on therapy at baseline (i.e. safety set). The frequency of patients with AEs,ADRs, and serious AEs will be also summarised by primary SOC and PT in each patient set.

The frequency of patients with ADRs and with serious AEs will be summarised by treatment (background medication and total), primary SOC and PT. AEs will also be reported by intensity.

To compare risks of overall ADR in different patient subgroups, frequency tabulation stratified by different patient subgroups will be provided with odds ratios and exact 95% confidence intervals whenever specified (see Section 6.4). Logistic regression will be used for odds ratio.

In addition, summaries for the time to onset of first episode for the ADRs will be tabulated, by duration (>0 to 12 weeks, >12 to 26 weeks, >26 to 40 weeks, >40 to 52 weeks, >52 to 64 weeks, >64 to 78 weeks, >78 to 104 weeks, >104 to 130 weeks, >130 to 156 weeks, >156 weeks, unknown), primary SOC, and PT.

An ADR is defined as an AE for which either the investigator or the sponsor (or both) assess the causal relationship to Trazenta[®] either as "Related," "Probably related," or "Cannot be denied". The SOCs will be sorted according to the standard sort order specified by European medicines agency, PTs will be sorted by frequency (within SOC).

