6.2.3 End of trial and follow-up period

The visit at 156 weeks after starting Trazenta® Tablets treatment or the last visit before discontinuation will be the end of the PMS. There is no follow-up period.

Proprietary confidential information © 2013 Boehringer Ingelheim International GmbH or one or more of its affiliated companies

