7.6 DETERMINATION OF SAMPLE SIZE

The sample size was determined based on the following: To detect an ADR with an incidence of 0.1% (or 0.16%) or greater in at least one patient with a probability of 95% (or 99%) or greater, at least 3,000 patients need to be entered and have at least one observation after treatment. According to the market survey for the patients with DPP-4 inhibitor, it is expected that 2010 patients with sulfonylurea, 1290 patients with biguanide, 840 patients with alpha glucosidase inhibitor, 510 patients with thiazolidinedione, and 90 patients with glinide will be entered, and the incidences of ADR in at least one patient with probability of 95% or greater are 0.15%, 0.24%, 0.36%, 0.59%, and 3.28% respectively.

In addition, according to the request from the Japanese authority, this PMS will target to include elderly patients, patients with renal dysfunction and hepatic dysfunction. The sample size for this patient subset was determined based on the following:

Elderly patients (>75 years)

U13-1769-01

Proprietary confidential information © 2013 Boehringer Ingelheim International GmbH or one or more of its affiliated companies

In a PMS of Micardis[®], an antihypertensive agent, for hypertensive patients (BI Trial No.: 502.511, Specified Drug Use Surveillance of Micardis [U11-1807-01]), 5,602 patients with diabetes mellitus were enrolled. Of the 5602 patients, 46.1% of the patients were <65 years, 33.1% of the patients were 65 to <75 years, and 20.8% of the patients were >=75 years.

Based on this assumption, more than 100 patients are highly likely to be collected in this PMS.

Renal dysfunction

In a PMS of Micardis[®] [U11-1807-01], 4,227 hypertention patients with diabetes mellitus and renal dysfunction were enrolled. According to their eGRF level, 52.4% of the patients were of mild renal dysfunction. 21.4% were moderate, 2.4% were severe, and 1.4% were end-stage, respectively. As this PMS plans to include a total of 3,000 patients, based on the above results of the Micardis[®] surveillance, it is estimated that numbers of patients included in this PMS and with mild, moderate, severe and end stage renal impairment will be about 1,572, 642, 72 and 42patients, respectively.

Based on this assumption, 140 patients with renal dysfunction including 30 end-stage patients are targeted to be included in this PMS.

Hepatic dysfunction

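### The ADR time-to-onset table states no denominator; under the SAP default its band percentages understate late risk among patients still at risk

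*SAP*

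**What the plan says.** SAP 7.8.1 plans that "summaries for the time to onset of first episode for the ADRs will be tabulated, by duration", crossed with primary SOC and PT. There are ten bands, from >0 to 12 weeks onward, ending ">78 to 104 weeks, >104 to 130 weeks, >130 to 156 weeks, >156 weeks, unknown". The section bases AE analyses on patients rather than events. For this table it names no percentage base, number at risk, person-time rate or life-table estimate.

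SAP 7 gives the general rule for percentages. Unless something else is specified, the base is "all patients in the respective patient set whether they have non-missing values or not". SAP 7.8.1 specifies nothing else for the onset table.

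Three further passages bear on who can contribute an onset:

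- Protocol 6.2.3 ends observation at week 156 or at the last visit before discontinuation, and adds: "There is no follow-up period".
- SAP 6.1 counts AEs as on treatment only up to 7 days after the last intake.
- SAP 7.7 tabulates exposure descriptively ("The followings are the categories of exposure-ranges (in weeks") with the same cut-points as the onset table.

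**The concern.** The protocol's objective is the safety of long-term daily use. In the available SAP text, this table is the only ADR output that shows how first-ADR risk develops over the 156 weeks.

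Two things get in the way of reading it like that. First, a patient who stopped in week 2 cannot have a first onset in >130 to 156 weeks, and neither can a patient who had that ADR in month 3. With the whole set as denominator, both still count there. Second, the bands are not equally wide, so a row can grow only because it covers more weeks.

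The risk is that attrition or band width is read as a change in ADR risk. In particular, a flat or rising late risk could be shown as a declining one.

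**Working it through.** **The plan's own figure.** Protocol 7.6 states that "at least 3,000 patients need to be entered and have at least one observation after treatment", so as to see "an ADR with an incidence of 0.1% (or 0.16%) or greater" in at least one patient "with a probability of 95% (or 99%) or greater". With P = 1 − (1 − p)^N:

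- 1 − 0.999^3000 = 95.03%
- 1 − 0.9984^3000 = 99.18%

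Both reproduce. They fix N = 3,000 for what follows and are not in dispute.

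**Band widths (SAP 7.8.1).** 12, 14, 14, 12, 12, 14, 26, 26 and 26 weeks, then an open-ended row.

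**Assumptions (not in the documents).** A constant first-ADR hazard h = 0.04 per year; a constant stopping hazard d = −ln(1 − annual stopping proportion), for 10, 20 and 30% per year; a year of 52 weeks.

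**Formulas.** Let k = h + d.

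- Share still on treatment and ADR-free at time t: S(t) = exp(−k·t)
- All-patients percentage for band (a, b]: (h/k) × [S(a) − S(b)]
- Risk over the band for a patient at risk at its start who does not stop: 1 − exp(−h(b − a))

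**Worked row, >130 to 156 weeks, 20% stopping per year.** d = 0.2231 and k = 0.2631. S(2.5 years) = 0.5180 and S(3 years) = 0.4541.

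- Table percentage: (0.04/0.2631) × 0.0639 = 0.97%, about 29 of 3,000 patients
- Conditional risk: 1 − exp(−0.04 × 0.5) = 1.98%
- Patients at risk at week 130: 3,000 × 0.518 = 1,554
- Patient-years in the band: 3,000 × 0.0639/0.2631, about 728; 29.1/728 = 4.0 per 100 patient-years, the rate that was put in

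**All rows at 20% stopping (%).** 0.90, 0.98, 0.91, 0.73, 0.69, 0.75, 1.26, 1.11, 0.97.

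| Stopping per year | On treatment at week 130 | First row (>0 to 12) | Last row (>130 to 156) | Conditional 26-week risk | Last row / conditional |
|---|---|---|---|---|---|
| 10% | 77% | 0.91% | 1.34% | 1.98% | 0.68 |
| 20% | 57% | 0.90% | 0.97% | 1.98% | 0.49 |
| 30% | 41% | 0.88% | 0.67% | 1.98% | 0.34 |

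**Separating the two effects.**

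- *Denominator.* The last three bands all span 26 weeks, so width plays no part among them. At 20% stopping they fall 1.26, 1.11, 0.97% although the hazard is flat. If the hazard instead rises by year from 4.0 to 4.5 to 5.0 per 100 patient-years, they still fall: 1.42, 1.37, 1.20%.
- *Width.* With nobody stopping, the first row is 1 − exp(−0.04 × 12/52) = 0.92% and the last is exp(−0.10) − exp(−0.12) = 1.79%, again with a flat hazard. At 20% stopping, the step from 0.75 to 1.26% at week 78 is likewise due to width alone. The wider bands enlarge late rows.

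**A second set of assumptions.** With a constant hazard giving 5 to 20% cumulative risk at 156 weeks, and 50 to 80% of patients retained, the last row is 0.44 to 0.78 of the conditional risk. It falls below the first row only when retention at week 156 is under about 44%, 46% or 52% (cumulative risk 5, 10 or 20%).

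**The case against.** The strongest reply is that SAP 7.8.1 promises only a tabulation of onset times. It may be meant to describe when the observed ADRs began, not interval risk. The all-patients base is inferred from a general default, and the internal AE guideline that SAP 7.8.1 cites, which was not available here, may say more. This stands as a caution: the point is what the visible plan implies, not what it states outright. It does not remove the problem. Dividing every band by any one fixed number leaves the pattern across bands unchanged, and so does printing counts alone.

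A reader might infer that the unequal bands help to understate late risk. They do the opposite. After week 78 the rows cover about twice as many weeks, so the raw last row exceeds the first at 10% and 20% stopping and drops below it only at 30%. The cut-points are also the protocol's observation times and are printed as row labels.

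A reader might also infer that the plan cannot address long-term ADR risk at all. That is too strong. SAP 7.7 uses the same cut-points, for the total and by background medication, so rough numbers still on treatment can be set beside the onset counts. They stay rough, because SAP 5.4 takes interruptions out of exposure and patients with an earlier ADR are not removed.

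Finally, the analyses are descriptive, and the primary safety endpoint, overall ADR incidence, does not come from this table. Both are true, and they limit the consequence.

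**Conclusion.** The point holds in a limited form. If the SAP 7 default applies, the band percentages understate late first-ADR risk among patients still at risk. Under the assumed 4 per 100 patient-years and 10 to 30% stopping per year, the last 26-week row shows about one-third to two-thirds of the conditional risk (0.67 to 1.34% against 1.98%). The direction follows from the design; the size rests wholly on assumed ADR and stopping rates.

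Band width is a separate defect, of comparability across week 78, and it pushes late rows up. The net visual trend is therefore indeterminate. The table does not by itself show how ADR risk develops over time. The documents do not support reading this as a bias in the overall ADR incidence or as a fault in the 3,000-patient sample size. It is a worthwhile, inexpensive improvement to one table that serves the stated long-term objective.

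**What to change.** In SAP 7.8.1, for any ADR and by SOC, add to each onset band:

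1. the number of patients on treatment and free of that ADR at the start of the band;
2. the on-treatment patient-years in the band among those patients, including the 7-day window of SAP 6.1 so that events and time match;
3. first ADRs per 100 patient-years, or the life-table conditional probability, with a 95% CI, beside the counts.

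State the denominator of any percentage that is kept. Leave onsets in the unknown row as counts.

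The existing bands can stay, because a rate removes the effect of width and the at-risk base removes the effect of attrition. Onset dates and treatment dates are already collected, and the cut-points match SAP 7.7, so no new data are needed. The cost is SAP wording, a small amount of programming and a wider table.
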